STUDY PROTOCOL

TITLE

A double-blind, randomized, placebo-controlled study to evaluate the efficacy of a homoeriodictyol mouthwash in chemotherapy-induced taste disorder – including a pilot study to evaluate taste testing during chemotherapy

Submitted by:

Assoc.-[name].-Doz. [name]

Dipl.-Ing. [name]

o.-Univ.-[name]. [name]

[name]

[name]

[name]

[name]

[name]

Corresponding author:

Assoc. [name].-Doz. [name]

Department of General Gynecology and Gynecologic Oncology

University Clinic for Gynecology

Medical University of Vienna

[name]

[contact]

[contact], [contact]

A) Scientific section

1. Summary

Background: More than 75% of women with cancer experience taste disorders during adjuvant chemotherapy. Bitter phantogeusia is particularly limiting. This can lead to impaired food intake with reduced energy intake, as well as changes in body composition, a reduced quality of life, and weight loss.

Study Objective: The objective of this study is, on one hand, to evaluate taste testing during chemotherapy and, on the other hand, to significantly reduce bitter phantogeusia by using a mouthwash containing homoeriodictyol (HED) immediately before consuming main meals. Taste testing during chemotherapy will be evaluated as part of a pilot study. In the controlled study, the primary endpoint is the measured reduction in the perception of bitterness from 500 ppm caffeine between week 1 and week 3. This is intended to improve food intake and body composition and counteract treatment-related weight loss.

Methods: As part of a pilot study, taste sensitivity is assessed before the start of chemotherapy and during chemotherapy. This phase of the study includes 40 patients undergoing chemotherapy. Taste sensitivity assessments are conducted before the start of chemotherapy and during the third cycle of chemotherapy, and blood samples are also collected. Food intake is assessed once a week using a 24-hour recall, and saliva samples are collected during the third cycle of chemotherapy. In the double-blind, randomized, placebo-controlled study, 32 patients with bitter phantogeusia will be included after completion of chemotherapy. Patients must rinse their mouths with a water solution containing HED (intervention group) or a placebo-containing water solution (control group) for 12 weeks immediately before consuming main meals. In weeks 1, 3, and 12, an evaluation of the taste disorder is conducted, and food intake is assessed using a 24-hour recall. In addition, the patients' body composition and weight are assessed in weeks 1 and 12. Furthermore, quality of life is measured using the EORTC-QLQ-30 Ovar and OV-28 in weeks 1, 3, and 12, and patient-related outcomes are recorded via a diary.

Conclusion: Aim of this study is to evaluate changes in taste perception during chemotherapy and to demonstrate a reduction in bitter phantogeusia following the use of a HED mouthwash in women with cancer undergoing chemotherapy.

2. Scientific knowledge

2.1. Background

Up to 77% of all female cancer patients suffer from chemotherapy-related taste disorder [1, 2]. On one hand, there is a loss of taste buds; on the other hand, tastes are perceived differently. This impairs the quality of life of oncology patients, and reduced appetite leads to decreased food intake, nutritional deficiencies, and, in the long term, increased mortality. The exact mechanism by which chemotherapeutic agents cause taste disturbances is currently not well understood [1], and no effective therapeutic interventions are available.

Cancer patients often experience a persistent bitter or metallic taste [3]. This taste disorder is called bitter phantogeusia and is associated with increased expression of the bitter receptors (TAS2Rs) 3, 42, and 43 in the taste cells of the tongue [4]. Tsutsumi et al. [5] demonstrated that patients with bitter phantogeusia who received a combination of radiation therapy and chemotherapy (cisplatin/5-fluorouracil) exhibited increased expression of TAS2R5. This effect was not observed with radiation therapy alone [5]. Furthermore, it was shown that bitter phantogeusia is more pronounced with cisplatin-containing chemotherapy, in contrast to combination therapy with cyclophosphamide, doxorubicin, or 5-fluorouracil. Nevertheless, the exact mechanism by which chemotherapy affects taste receptors is highly complex and poorly understood, which is why no effective treatments for bitter phantogeusia are currently available.

The plant-derived compound homoeriodictyol (HED) can reduce the perception of the bitter taste of caffeine by approximately 40% [7] and is currently one of the most potent bitter-masking agents. HED acts as an antagonist on the bitter receptors TAS2R20, 31, 43, and 50 [8]. In addition, it has been shown that a 30 mg bolus dose of HED has an appetite-stimulating effect in healthy subjects [9]. This amount of HED is already used by the food industry to mask bitter tastes.

We hypothesize that HED can help cancer patients who have undergone chemotherapy regain a normal sense of taste and stimulate their appetite, which may lead to increased food intake. Furthermore, preliminary results from our research group indicate that HED has a pro-proliferative effect on buccal cells and taste cells treated with cisplatin or 5-fluorouracil. This suggests that HED could help accelerate the regeneration of taste cells following chemotherapy, even though the cellular signaling pathways affected by HED are not yet known.

3. Rationale and Project Objectives

3.1 Rationale

More than 75% of women with ovarian cancer experience taste disturbances during adjuvant chemotherapy. This can lead to impaired food intake, reduced energy intake, and an unfavorable body composition, resulting in weight loss.

3.2 Project Objectives

The objective of the pilot study is to evaluate taste changes during chemotherapy. The objective of the placebo-controlled trial (RCT) is to significantly counteract taste disturbances by using a mouthwash containing homoeriodictyol (HED) immediately before consuming main meals. The primary endpoint is the measured reduction in the perception of bitterness. This is intended to improve food intake and body composition and counteract treatment-related weight loss.

3.3 Study Endpoints

Pilot Study

- Comparison of taste tests before and during chemotherapy

RCT

Primary endpoint:

- Comparison of the perception of bitterness induced by 500 ppm caffeine from week 1 to week 3 between the study group (HED mouthwash) and the control group (water mouthwash).

Secondary endpoints:

- Comparison of the perception of bitterness triggered by 500 ppm caffeine from week 1 to week 12 between the two groups.
- Comparison of the threshold for bitterness perception from week 1 to week 3 between the two groups.
- Comparison of the threshold for bitter taste perception in week 3 between the two groups.
- Comparison of overall taste perception in week 3 between the two groups.
- Comparison of overall taste perception from week 1 to week 12 between the two groups.
- Comparison of food intake using a 24-hour recall from week 1 to week 12 within the two groups.
- Comparison of food intake using a 24-hour recall from week 1 to week 12 between the two groups.
- Comparison of improvements in body composition from week 1 to week 12 between the two groups.

- Comparison of weight gain from week 1 to week 12 between the two groups.
- Comparison of quality of life using the EORTC-QLQ-30 Ovar and OV-28 from week 1 to week 12 within the two groups.
- Comparison of the change in quality of life using the EORTC-QLQ-30 Ovar and OV-28 from week 1 to week 12 between the two groups.
- Comparison of “patient-related outcomes” using a diary from week 1 to week 12 within the two groups.

4. Experimental Protocol

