4.1. Study Design

Pilot Study

This part of the study will include 40 female patients undergoing chemotherapy. Taste tests will be conducted before the start of chemotherapy and during the third cycle of chemotherapy. At these time points, blood samples will also be collected to determine zinc levels and the concentration of the chemotherapeutic agent, and a baseline medical history and taste-specific medical history will be assessed via questionnaire. Food intake is assessed once a week using a 24-hour recall, and during the third cycle of chemotherapy, saliva samples are additionally collected to serially evaluate the concentration of the chemotherapeutic agent in saliva.

RCT

This study is a double-blind, randomized, placebo-controlled trial investigating the effect of rinsing the mouth with HED before each main meal on the perception of bitterness over a 12-week period following completion of chemotherapy. Due to their prior treatments, patients undergo a detailed examination, including physical examination and preanesthetic assessment. In addition, a taste perception test is performed as part of the screening process. Furthermore, adverse events are reported during each chemotherapy cycle. In addition, a taste perception test is conducted as part of the screening process to identify any pre-existing taste disorders. If a general taste disorder is ruled out and an isolated disturbed perception of bitterness is confirmed, the patient can be included in the study.

A total of 32 patients will be included in the study (study group: 16 patients, placebo group: 16 patients). Depending on randomization, patients receive either a mouthwash containing HED and water or a mouthwash containing food coloring and water. In weeks 1, 3, and 12, an evaluation of bitter perception triggered by 500 ppm caffeine, a determination of the bitter perception threshold, and food intake assessment via a 24-hour recall questionnaire are conducted. In addition, at the same time points, the patients' quality of life is assessed using the EORTC-QCQ-30 Ovar and the OV-28 questionnaire. In addition, the patients' body

composition and weight will be assessed in week 1 and week 12. Patient-reported outcomes will be recorded using diaries.

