The patient returns for screening one week after her last cycle of chemotherapy due to suspected bitter phantogeusia. The patient's bitter phantogeusia is determined by directly asking about bitter taste perception ("Did you notice an increased bitter taste during the course of chemotherapy?") and subsequently classifying the increased perception as "mild," "moderate," or "severe." If the patient rates her heightened perception of bitterness as "moderate" or "severe," meets all inclusion and exclusion criteria, and consents to the study by signing the patient information form, she is eligible for inclusion in the study. As part of the screening examination, the threshold for bitter perception and the bitter perception triggered by 500 ppm caffeine are recorded. Body composition is also measured using the BOD POD® and a weight check is performed. Quality of life is assessed using the EORTC-QLQ-30 Ovar and OV-28, and dietary intake is assessed using a 24-hour recall questionnaire (GloboDiet). In addition, perception of the other four basic tastes (sweet, sour, salty, umami) is determined using a sensory test. Furthermore, the patient is given a detailed explanation of the necessary follow-up visits required as part of the study and is handed a diary.

Visit 2

The patient returns for a follow-up visit three weeks after the end of her last course of chemotherapy. A test is conducted to assess bitterness perception of 500 ppm caffeine and to determine the bitterness perception threshold, as well as a sensory test to assess perception of the taste qualities sweet, sour, salty, and umami, a quality-of-life assessment using the EORTC-QLQ-30 Ovar and OV-28, and a dietary intake assessment using the 24-hour recall questionnaire (GloboDiet).

Visit 3

The patient returns 12 weeks after the end of her last chemotherapy session for a final examination. A test of bitterness perception using 500 ppm caffeine and determination of the bitterness perception threshold is performed, along with a sensory test to assess perception of the taste qualities sweet, sour, salty, and umami, a measurement of body composition using the BOD POD®, and a weight check. Quality of life is assessed using the EORTC-QLQ-30 Ovar and OV-28, and dietary intake is assessed using a 24-hour recall questionnaire (GloboDiet). The diary is discussed and collected.

RCT: Overview of Study Visits

	CRF	QoL (EORTC 30 and OV-28)	Medication dispense/return	Sensory test	BOP POD	Weight	Diary	24-hour recall

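### Overall taste at week 3 is listed only as a between-group level, a second week-3 threshold line is redundant, and the week-12 bitter threshold has no listed endpoint

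*Combined protocol and SAP*

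**What the plan says.** Section 3.3 treats three taste measures in the RCT. Caffeine bitterness is compared from week 1 to week 3 (primary) and from week 1 to week 12 (secondary). The bitter threshold has two secondary lines: "Comparison of the threshold for bitterness perception from week 1 to week 3 between the two groups" and then "Comparison of the threshold for bitter taste perception in week 3 between the two groups". Overall taste perception also has two: "Comparison of overall taste perception in week 3 between the two groups" and "Comparison of overall taste perception from week 1 to week 12 between the two groups".

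The data behind these lines are collected at all three visits. Section 4.1 sets the schedule: "In weeks 1, 3, and 12, an evaluation of bitter perception triggered by 500 ppm caffeine, a determination of the bitter perception threshold". Section 4.1.1 confirms the threshold at the final visit: "A test of bitterness perception using 500 ppm caffeine and determination of the bitterness perception threshold is performed". For the other tastes, it says of Visit 1 that "perception of the other four basic tastes (sweet, sour, salty, umami) is determined using a sensory test", and it repeats the sensory test at Visits 2 and 3. Under section 4.3.3 the taste test comes before randomisation, so the Visit 1 values are true baselines.

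Sections 4.4.1 and 4.4.2 add, in general terms, that threshold and taste results will be compared across arms and visits. The Statistical Section (B), item 3, plans Student's t or Mann-Whitney tests for metric variables and names no baseline covariate.

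**The concern.** Caffeine bitterness has a regular pair of contrasts, and the other two taste measures break that pattern in different ways. Overall taste at week 3 is compared without reference to each patient's own starting value, although that value is on file. The threshold gets two lines on the same week-3 data and none on week 12.

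Two things are at stake. In a trial of 32 patients, randomised with neither strata nor blocks, a comparison that leaves out an available baseline keeps between-patient variation it could have removed. And a threshold result after the full 12 weeks of rinsing would belong to no listed endpoint, so its standing in the report would be open to dispute. The background gives some reason to want it: "This suggests that HED could help accelerate the regeneration of taste cells following chemotherapy".

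**Working it through.** **Endpoints set side by side (section 3.3)**

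| Measure | Week 1 to 3 | Week 3 level | Week 1 to 12 |
|---|---|---|---|
| Caffeine bitterness | primary | none | secondary |
| Bitter threshold | secondary | secondary | none |
| Overall taste | none | secondary | secondary |

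All three measures are taken at Visits 1, 2 and 3, so each empty cell in the two change columns could be filled from data already planned. The threshold's week-3 level uses only part of the data that the line above it uses.

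**Precision of the week-3 comparison.** The plan gives no figure for this point, so there is none to reproduce.

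Inputs from the documents: 16 per arm, and 20% dropout, which leaves 16 × 0.8 = 12.8, or about 13 per arm. Input assumed: the correlation r between week-1 and week-3 values, which the documents do not give; the range 0.3 to 0.8 is shown. A metric score with equal SD at both visits is also assumed.

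The standard error of the between-group difference, in SD units, is sqrt((2/n) × v), where v is:
- level at week 3: v = 1
- plain change score: v = 2(1 − r)
- ANCOVA on the Visit 1 value: v = 1 − r²

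For the level, sqrt(2/16) = 0.35 SD, and sqrt(2/13) = 0.39 SD with 13 per arm. For ANCOVA with 16 per arm at r = 0.5, sqrt(0.125 × 0.75) = 0.31 SD; at r = 0.7, sqrt(0.125 × 0.51) = 0.25 SD.

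| r | v, change | SE, change (16 / 13 per arm) | v, ANCOVA | SE, ANCOVA (16 / 13 per arm) |
|---|---|---|---|---|
| 0.3 | 1.40 | 0.42 / 0.46 | 0.91 | 0.34 / 0.37 |
| 0.5 | 1.00 | 0.35 / 0.39 | 0.75 | 0.31 / 0.34 |
| 0.7 | 0.60 | 0.27 / 0.30 | 0.51 | 0.25 / 0.28 |
| 0.8 | 0.40 | 0.22 / 0.25 | 0.36 | 0.21 / 0.24 |

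The change score is more precise than the level only when 2(1 − r) < 1, that is, r > 0.5. ANCOVA has the smaller variance across the whole range.

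**In terms of power.** With 13 per arm, a true difference of 1 SD and a two-sided 5% test (level assumed), power is about 69% for the week-3 level. With ANCOVA it is about 73%, 81%, 93% and 98% at r = 0.3, 0.5, 0.7 and 0.8. These figures ignore the one degree of freedom spent on the covariate.

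**The case against.** The strongest reply is that little is lost. A week-3 comparison between randomised, blinded arms is valid. The lines concerned are unranked secondary endpoints, and the primary endpoint is untouched. Sections 4.4.1 and 4.4.2 already promise comparisons across visits. Patients with a general taste disturbance at baseline are excluded, which could narrow the week-1 range of overall taste, lower r and shrink the gain. Section 4.4.2 says only that patients rate the quality of each taste, so the score may not be metric. And rewording to a change from week 1, under a plan that offers only t or Mann-Whitney tests, would naturally be run as a change score, which at r = 0.3 is worse than the level.

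Most of this stands, and it limits the point. It does not remove it: the general promise in 4.4.1 and 4.4.2 names no contrast and no time point, and the change-score problem is a reason to name the analysis method as well as the contrast.

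A reader might also infer four stronger things that the documents do not support.
- *That the threshold's baseline is thrown away.* It is not; the line from week 1 to week 3 uses it. Overall taste also uses its baseline in the week 1 to week 12 line.
- *That the week-3 level is biased by chance imbalance.* With 16 per arm, a baseline difference above 0.5 SD has a probability of about 16% (0.5/0.354 = 1.41 standard errors), but the unadjusted standard error already reflects that variation. It is not a further cost.
- *That the week-12 threshold will go unanalysed.* The plan says only that it is compared in general terms; what it lacks is a line in 3.3.
- *That regeneration must show late.* The background speaks of acceleration, which could equally appear early, with placebo patients catching up.

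**Conclusion.** The point holds in a limited form. Section 3.3 has no baseline-referenced week-3 line for overall taste, one redundant week-3 line for the threshold, and no line for the week-12 threshold. One measure, not two, lacks a week-3 comparison that uses the baseline.

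The cost is precision and clarity, not validity. With 16 per arm, covariate adjustment would cut the standard error by about 13% at r = 0.5 (0.35 to 0.31 SD) and about 29% at r = 0.7 (0.35 to 0.25 SD), but only about 5% at r = 0.3. These figures rest on assumed correlations and a metric score, and overall taste may sit at the lower end because of the baseline exclusion. This is an inexpensive improvement to secondary endpoints, not a flaw that threatens the trial's main conclusion.

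**What to change.** 1. In section 3.3, change the line on the bitter threshold at week 3 to a between-group comparison from week 1 to week 12.
2. In section 3.3, change the line on overall taste at week 3 to a between-group comparison from week 1 to week 3.
3. In the Statistical Section (B), item 3, state that where the bitter threshold and overall taste are scored on a metric scale, the arms are compared by ANCOVA with the Visit 1 value as covariate, not by a plain change score. With that covariate in the model, analysing the follow-up value or the change from Visit 1 gives the same treatment estimate, so the reworded lines and the method agree.

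The cost is two endpoint lines and one sentence on analysis, made by written amendment. The number of listed secondary endpoints does not change, and no visit, measurement or patient is added.

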4.1.2. Withdrawal from the study

Patients may withdraw from the study at any time without providing a reason. Withdrawal is defined as premature termination of the study prior to attending Visit 3. Every withdrawal is documented. Documentation up to the point of withdrawal must be complete. Patients who withdraw from the study will not be replaced. Patients who withdraw from the study will be included in the statistical analysis (intention-to-treat analysis). Patients who withdraw from the study must return all remaining study medication and will continue regular follow-up after gynaecologic cancer treatment at the Medical University of Vienna.

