4.1.5. Evaluation of efficacy

This is done by testing the perception of bitterness triggered by 500 ppm of caffeine in week 1 and week 3.

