The efficacy of the treatment is defined as a reduction in the perception of bitterness by more than 30% in the treatment group compared to the placebo group. The primary endpoint will be evaluated using a paired t-test.

This will be evaluated in two analyses:

- Intention-to-treat analysis: Inclusion of all patients who used the mouthwash at least once
- Per-protocol analysis: Inclusion of patients who completed the study according to the study protocol

Secondary endpoints are also analysed using intention-to-treat and per-protocol analyses. The collected clinical and pathological data are presented descriptively using absolute values or, depending on the normality of the distribution, using the median (interquartile range) or mean (standard deviation). Metric variables are compared using Student's t-test or the Mann-Whitney U test, depending on normal distribution. Categorical variables are compared using the chi-square test and, if feasible given the number of groups, presented including the odds ratio (95% confidence interval). The study will investigate predictive factors for response to the intervention. These analyses are performed using a multivariate binary logistic regression model. The following variables are included: patient age, number of chemotherapy cycles, patient BMI, bowel resection during the primary surgery, peripheral polyneuropathy during chemotherapy, nausea at the time of study enrolment, and diarrhoea at the time of study enrolment. Version 21.0 of the statistical software SPSS (SPSS, Inc.) is used for the statistical analysis.

Patient data is pseudonymized, documented, and analysed in accordance with current data protection regulations and is not disclosed to third parties. The data is published in anonymized and aggregated form.

C) Ethical and Legal Section

1. Ethical Aspects

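### Quality of life and food intake are compared only from week 1 to week 12 with no missing-data method, so patients who withdraw before Visit 3 cannot enter tests that the plan says include them

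*Combined protocol and SAP*

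**What the plan says.** **Measurement.** The Methods part of the Summary states that "quality of life is measured using the EORTC-QLQ-30 Ovar and OV-28 in weeks 1, 3, and 12". The same paragraph, section 4.1 and the RCT visits in section 4.1.1 give the same three times for the 24-hour food recall and the taste tests. Body composition and weight are measured only at weeks 1 and 12.

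**Endpoints (section 3.3, RCT).** Every quality-of-life and food-intake endpoint, within or between groups, runs from week 1 to week 12. The between-group quality-of-life endpoint reads "Comparison of the change in quality of life using the EORTC-QLQ-30 Ovar and OV-28 from week 1 to week 12 between the two groups". Bitterness is handled differently. Its primary contrast is "Comparison of the perception of bitterness induced by 500 ppm caffeine from week 1 to week 3 between the study group" and the control group, and a separate secondary endpoint is "Comparison of the perception of bitterness triggered by 500 ppm caffeine from week 1 to week 12 between the two groups". The bitterness threshold is compared only up to or at week 3, and overall taste is compared both at week 3 and from week 1 to week 12.

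**Withdrawal and analysis sets.** Section 4.1.2 defines withdrawal as stopping before Visit 3 is attended, rules out replacement, and says: "Patients who withdraw from the study will be included in the statistical analysis (intention-to-treat analysis". Section B.3 defines the intention-to-treat set as everyone who used the mouthwash at least once and adds: "Secondary endpoints are also analysed using intention-to-treat and per-protocol analyses".

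**Methods.** For metric variables, section B.3 names Student's t-test or the Mann-Whitney U test. Neither document section on analysis gives an imputation rule, a repeated-measures model or any other treatment of missing values. Section B.1 allows for 20% dropout.

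**The concern.** A two-group test of change from week 1 to week 12 needs both values for every patient. By the plan's own definition a withdrawn patient lacks the second one. Following the plan as written would therefore give results for completers under an intention-to-treat label.

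If women who do worse leave, and do so differently in the two arms, the week-12 comparisons are biased. For quality of life and food intake, the week-3 values are collected but enter no listed endpoint, so the data that could best inform the missing week-12 values go unused.

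**Working it through.** **1. Which endpoints are affected.** Of the 12 RCT secondary endpoints in section 3.3, three use week 3 (two on the threshold, one on overall taste) and nine end at week 12.

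| Outcome | Measured at weeks | Compared in section 3.3 | Affected |
|---|---|---|---|
| Quality of life | 1, 3, 12 | 1 to 12 only | yes |
| Food intake | 1, 3, 12 | 1 to 12 only | yes |
| Bitterness, 500 ppm caffeine | 1, 3, 12 | 1 to 3 (primary); 1 to 12 (secondary) | secondary only |
| Overall taste | 1, 3, 12 | at 3; 1 to 12 | week-12 contrast only |
| Bitterness threshold | 1, 3, 12 | 1 to 3; at 3 | no |
| Body composition, weight | 1, 12 | 1 to 12 | yes, with no week-3 value to use |

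The ninth week-12 endpoint, the diary outcomes, is compared within groups only and is left aside here.

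**2. How many patients.** The plan gives no figure for missing week-12 data, so its general dropout allowance is used. Inputs from section B.1: 32 patients, 16 per arm, 20% dropout.

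- Without week 12: 32 × 0.20 = 6.4, or 3.2 per arm.
- With week 12: 32 × 0.80 = 25.6, or 12.8 per arm.

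The total of 32 is taken as given. It does not follow from the stated inputs: a two-sample t-test with difference 30, SD 10, two-sided 1% and 90% power needs 6 per arm, 8 after dropout, 16 in all. That mismatch concerns the primary endpoint and does not bear on this point.

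**3. How many of them have week 3.** The documents do not say when dropout occurs. If 0%, 50% or 100% of dropouts leave after Visit 2 (assumption), then 0, 3.2 or 6.4 of them have a week-3 value.

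**4. Bias.** An arm's full mean is 0.8 × (completer mean) + 0.2 × (dropout mean). The completer mean is therefore off by 0.2 × d, where d is the completer mean minus the dropout mean. The between-group difference is off by 0.2 × (d in the HED arm − d in the control arm). This is zero if dropouts differ from completers equally in both arms. The documents give no value for d.

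**5. Precision.** Let m be the patients per arm with week 12, n those with week 3, and r the week 3 to week 12 correlation (assumed 0.6–0.8). In units of the outcome variance, and before allowing for baseline:

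- completers: 1/m = 1/12.8 = 0.0781
- using week 3: (1 − r²)/m + r²/n

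With dropout even over 12 weeks and Visit 2 two weeks after Visit 1, 10/12 of the 3.2 leave after Visit 2, so n = 12.8 + 2.67 = 15.47.

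| Dropouts with week 3 | n | r = 0.6 | r = 0.8 | Variance reduction |
|---|---|---|---|---|
| none | 12.8 | 0.0781 | 0.0781 | 0% |
| half | 14.4 | 0.0750 | 0.0726 | 4–7% |
| even over time | 15.47 | 0.0733 | 0.0695 | 6–11% |

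On the standard error the last row is a gain of about 3–6% (1 − √0.938 and 1 − √0.890). These are large-sample figures for a week-12 arm mean. The further gain once week 1 is in the model would differ.

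**The case against.** Four objections have force.

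- **Bitterness.** A reader might infer that bitterness too is analysed only at week 12. The documents do not support this. Section 4.1.5 says of efficacy: "This is done by testing the perception of bitterness triggered by 500 ppm of caffeine in week 1 and week 3". The threshold endpoint is likewise "Comparison of the threshold for bitterness perception from week 1 to week 3 between the two groups". A patient who leaves after Visit 2 still contributes to both.
- **Cause.** A reader might infer that leaving week 3 unused is what excludes withdrawn patients. It is not. They are lost because the week-12 value is missing and no method deals with that; unused week-3 data only removes one remedy. The plan is also silent rather than prescribing complete cases, and a simple test could follow imputation. But no imputation is planned, so the stated tests cannot take these patients as things stand.
- **Timing and size.** It is tempting to assume that most dropouts will have a week-3 value, or to quote a 7–13% variance reduction. The first depends on timing that the documents do not give. The second needs every dropout to have week 3 (n = 16 gives 0.0725 and 0.0681). The 20% also sits in a calculation for an endpoint that ends at week 3. If it means loss by week 3, those patients have no week-3 value, and about 6 is a minimum for week 12.
- **Remedy.** A mixed model does nothing for body composition and weight, rests on model assumptions with 16 per arm, and is not the only defensible choice. All of this stands, and the fix is limited accordingly.

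What remains is the conflict between promised inclusion and tests that cannot include.

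**Conclusion.** The point holds for quality of life and food intake, and for the secondary week 1 to week 12 tests of bitterness and overall taste. It does not touch the primary endpoint or the threshold endpoints.

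About 6 of 32 patients are affected, on the assumption that the 20% dropout describes loss by week 12. The main harm is possible dropout bias in results labelled intention-to-treat; its size cannot be derived from the documents. The precision at stake is minor, from zero to about 6–11% of variance under the stated assumptions on timing and correlation. This is a worthwhile improvement to secondary analyses, not a threat to the trial's main conclusion.

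**What to change.** In section B.3, for the week-12 between-group comparisons of quality of life, food intake and bitterness (and overall taste if it is scored numerically), replace the simple test of change with one mixed model for repeated measures per outcome. Use weeks 1, 3 and 12 as the repeated measures, with arm-by-visit terms. Report the week-12 between-group difference with its confidence interval.

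State that the analysis assumes missing at random. Add a simple sensitivity analysis, for example worsening the assumed week-12 values of withdrawn patients by a range of fixed amounts. Say plainly that patients who leave before Visit 2 add little to the week-12 estimate.

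Leave the timing of the primary endpoint and of the week-3 threshold endpoints as it is. For body composition and weight, either label the result as an analysis of completers or state a missing-data method.

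The cost is analysis wording and slightly more programming, which the named software supports, plus reliance on model assumptions in a small trial. No new visits, patients or data are needed.
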